The Oswestry Low Back Pain Questionnaire is contained in **Appendix D**.

RANGE OF MOTION (ROM)

The subject's ROM measurements for flexion, extension, left lateral flexion and right lateral flexion will be taken using a goniometer and following the American Medical Association Guides (2nd and 4th editions) recommendation using measurements of thoracolumbar and lumbar range of movement, respectively, to estimate the percentage of impairment in patients with chronic low back pain. These measurements evaluate the mobility of the lumbar spine from both an articular and a muscular standpoint.

The table below shows the normal measurement values in degrees for each ROM location.

| Measurement | Normal |
|-----------------------|----------|
| Flexion | 60 degs. |
| Extension | 25 degs. |
| Left Lateral Flexion | 25 degs. |
| Right Lateral Flexion | 25 degs. |

SUBJECT DAILY DIARY

Throughout the duration of a subject's participation in this clinical study, from study entry through to the final post-procedure administration visit, inclusive, the subject is required to maintain a Subject Daily Diary. On each day of the study, the subject will record the following information in the Subject Daily Diary, as is applicable:

- ✓ **Rescue Pain Medication Use:** The subject will record each time a dose of the study rescue pain medication is taken as needed to manage low back pain.
- ✓ **Other Pain Medication Use:** The subject will record each time a dose of pain medication other than the study rescue pain medication is taken to manage low back pain. The subject, will,

however, have been instructed to take only the study rescue medication for low back pain relief during the duration of study participation, but deviations are to be recorded.

- ✓ **Other Pain Management Use:** The subject will record each time any treatment, therapy or other means of low back management that is not an OTC or a prescription medication is applied to manage his or her low back pain. The subject, will, however, have been instructed to not engage in any other therapeutic applications for low back pain relief other than the study rescue medication for low back pain relief during the duration of study participation, but deviations are to be recorded.

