- Subject is willing and able to refrain from consuming any over-the-counter and/or prescription medication and/or herbal supplements intended for the relief of pain and/or inflammation, including muscle relaxants throughout the course of study participation, except for the specified study pain relief medication
- Subject is willing and able to refrain from engaging in any non-study procedure therapies for the management of his or her low back pain throughout the course of study participation, including

conventional therapies such as physical therapy, occupational therapy and hot or cold packs, as well as alternative therapies such as chiropractic care and acupuncture

- Subject agrees and is able to complete the Subject Daily Diary, as applicable, throughout the course of his or her participation in the study
- 18 years of age or older
- Male or female
- Subject's primary language is English

EXCLUSION CRITERIA

A subject who satisfies any of the following criteria will be excluded from study participation:

- The subject's presenting primary pain is located outside or in addition to the region of the lower back, right and/or left side(s); that is, on the region of the back above the lowest rib and/or below the crease of the buttocks
- Subject's low back pain is undiagnosed, or has been diagnosed by a qualified medical professional as being other than that of benign musculoskeletal origin wherein the etiology is lumbar sprain or strain - a stretch injury to the ligaments, tendons, and/or muscles of the low back - that occurs in the absence of any serious underlying pathology or nerve root compromise
- Subject's low back pain has been diagnosed by a qualified medical professional as being in whole or in part due to one or more of the following origins, or any one or more of the following etiologies of the subject's low back pain cannot be satisfactorily ruled out:
 - ✓ *Mechanical*: such as apophyseal osteoarthritis; diffuse idiopathic skeletal hyperostosis; degenerative discs; Scheuermann's kyphosis; s ("slipped disc"); thoracic or lumbar spinal stenosis; spondylolisthesis and other congenital abnormalities; fractures; leg length difference; restricted hip motion; misaligned pelvis - pelvic obliquity; anteversion or retroversion; and abnormal foot pronation
 - ✓ *Inflammatory*: seronegative spondylarthritides (e.g. ankylosing spondylitis); rheumatoid arthritis; infection - epidural abscess or osteomyelitis

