- Subject's presenting low back pain is not episodic chronic, defined as one or more of the following being present:
 - ✓ lower back pain has not been ongoing over at least the preceding three months or has been ongoing for less than the preceding 3 months
 - ✓ lower back pain has occurred on less than 15 days of each of the preceding 3 months
 - ✓ each individual episode of lower back pain over the preceding 3 months has lasted for a period of less than 24 hours
 - ✓ period of time between individual episodes of lower back pain over the preceding 3 months has been less than 24 hours
- Subject's self-reported Degree of Pain rating on the VAS pain scale is less than 40
- Use of any one or more of the following analgesics, or an equivalent, within 7 days prior to commencement of administration of the study procedure protocol with the Erchonia® FX-635™:
 - ✓ paracetamol
 - ✓ Compound analgesics
 - ✓ Topical analgesics: patches, creams and lotions

N.B.: If any of the above analgesics have been taken within 7 days prior to commencement of administration of the study procedure protocol, the subject will remain eligible for study participation if he or she agrees to refrain from use of the analgesic(s) for 7 days prior to commencement of study procedure administration.

- Use of the following muscle relaxants within the prior 30 days:
 - ✓ cyclobenzaprine (Lexeril, Fexmid)
 - ✓ diazepam (Valium)
 - ✓ meprobamate (Miltown®, Equinil®, Equagesic®, Meprospan®)

N.B.: If any of the above muscle relaxants have been taken within 30 days prior to commencement of administration of the study procedure protocol, the subject will remain eligible for study participation if he or she agrees to refrain from use of the muscle relaxant(s)

until 30 days of non-use prior to commencement of study procedure administration has been attained.

- Use of any of the following muscle relaxants within 7 days prior to commencement of administration of the study procedure protocol with the Erchonia® FX-635™:
 - ✓ Carisoprodal (Soma®, Sodal®, Soprodol®, Soridol®)
 - ✓ Metaxalone (Skelaxin, Robaxin)

N.B.: If any of the above muscle relaxants have been taken within 7 days prior to commencement of administration of the study procedure protocol, the subject will remain eligible for study participation if he or she agrees to refrain from use of the muscle relaxant(s) until 7 days of non-use prior to commencement of study procedure administration has been attained

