 10. Building up a tolerance to the alcohol or drug. Tolerance is defined by the DSM-5 as “either needing to use noticeably larger amounts over time to get the desired effect or noticing less of an effect over time after repeated use of the same amount.”
 11. Experiencing withdrawal symptoms after stopping use of a substance that can be relieved by taking more of the substance. According to the DSM-V definition and criteria, key ‘withdrawal symptoms’ include: ‘anxiety, irritability, fatigue, nausea/vomiting, hand tremor or seizure in the case of alcohol.’

Evaluation for satisfaction of the DSM-V ‘substance use disorder’ criteria will be conducted both with respect to the preceding 12 month period (current abusers) and with respect to any 12-month period in the past (history of prior abuse).

- Developmental disability or cognitive impairment that in the opinion of the investigator would preclude adequate comprehension of the informed consent form and/or ability to record the necessary study measurements
- Involvement in litigation and/or receiving disability benefits related in any way to the parameters of the study

- Subject is less than 18 years of age
- Participation in a clinical study or other type of research in the past 30 days
- Subject's primary language is other than English

WASHOUT PHASE: 48 HOURS PRIOR TO COMMENCEMENT OF THE PRE-PROCEDURE EVALUATION PHASE

The pre-procedure washout phase comprises the 48-hour period immediately preceding the pre-procedure evaluation phase, beginning upon waking on the first 24-hour period.

At the start of the pre-procedure washout phase, the subject commences his or her required abstinence from use of non-study related medications and therapies for the relief of his or her low back pain and also commences the as-needed consumption of the study rescue medication for his or her low back pain that will continue through to the end of the post-procedure evaluation phase.

WASHOUT PHASE MEASURES

On each day of the two-day pre-procedure Washout Phase, the subject records the following measures, as outlined in the STUDY TEST BATTERY section above.

- Subject Daily Diary (all applicable measures)
- Visual Analog Scale (VAS) Degree of Pain Rating: recorded upon waking on each morning of the two-day pre-procedure Washout Phase

CONFIRMATION OF CONTINUED SUBJECT STUDY ELIGIBILITY

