While the results of this study demonstrated statistically significant efficacy of Erchonia active laser treatment over placebo, the effect (the clinically meaningful pain reduction outcome) appeared to develop at a slower rate over a longer period of time than that which had been demonstrated in prior Erchonia Corporation clinical studies for pain reduction indications such as for neck and shoulder pain (K100509) and for chronic heel (plantar fasciitis) pain (K132940), indicating that the condition of chronic low back pain is a more resistant to therapy than the other chronic pain conditions previously evaluated and therefore necessitates a slightly enhanced procedure administration protocol that does not increase the risk to the subject nor compromise subject safety in any way in its implementation.

Therefore, it was decided that slight increments in and modifications to each of the procedure administration outputs variables was warranted to attain a comparable treatment effect for the reduction of chronic low back pain as had been attained in prior Erchonia Corporation pain reduction clinical trials, as shown in the comparative table below:

| Treatment Parameter | Initial Trial Treatment Parameter | Modified Current Output Treatment Parameter |
|-------------------------------------------|------------------------------------------|----------------------------------------------------|
| Number of Treatments | 6 | 8 |
| Duration of Treatment Administration | 3 weeks | 4 weeks |
| Frequency of Treatment Administration | 2 times per week | 2 times per week |
| Duration of Each Procedure Administration | 15 minutes | 20 minutes |

PROCEDURE ADMINISTRATION PHASE MEASURES

DAILY MEASURES

Commencing on the same day as the first study procedure administration with the Erchonia® FX-635™, the subject begins to record all of the required information in the Subject Daily Diary, as applicable, at home, and continues to satisfactorily complete the Subject Daily Diary through each day of the procedure administration phase.

The rescue pain medication (OTC Tylenol) use count on day one of the procedure administration phase will serve as the subject’s initial (baseline) pain medication count for the purpose of subsequent evaluation of change in utilization of pain relief medication throughout study participation.

FOLLOWING EACH PROCEDURE ADMINISTRATION

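### Baseline rescue-medication use is a single count from the first-session day, after randomization, so it can include post-session doses; the two washout diary days offer a cleaner baseline

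*Combined protocol and SAP*

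**What the plan says.** The baseline rule is under Procedure Administration Phase Measures, Daily Measures: "The rescue pain medication (OTC Tylenol) use count on day one of the procedure administration phase will serve as" the starting value for judging change in pain-relief use over the rest of participation. The sentence before it dates that phase's diary: "Commencing on the same day as the first study procedure administration", "the subject begins to record all of the required information in the Subject Daily Diary".

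Other sections place rescue use and its recording earlier. Under Washout Phase, the subject stops other remedies and "also commences the as-needed consumption of the study rescue medication for his or her low back pain". Washout Phase Measures and the Table of Subject Events have the diary kept in the two-day washout. Subject Daily Diary requires it "from study entry through to the final post-procedure administration visit, inclusive, the subject is required to maintain a Subject Daily Diary", and on content says "The subject will record each time a dose of the study rescue pain medication is taken as needed to manage low back pain".

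Confirmation of Continued Subject Study Eligibility takes baseline VAS as the average of the two washout ratings. Randomization follows that confirmation and precedes the pre-procedure evaluation and the first session.

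Evaluation of Rescue Pain Medication Use plans descriptive statistics and qualitative comparisons only.

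**The concern.** A baseline for change should be fixed before treatment can act on it. This one is counted on a day that includes the first session, after allocation. If the arms responded differently on that day, part of the response would sit in the baseline and be subtracted from every later comparison. The protocol already schedules recording of each rescue dose on two days before randomization, when the arms can differ only by chance. It uses that window for baseline VAS, but not for rescue use, and gives no reason for the difference.

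What is at stake is how the change in rescue use is read, in a trial where rescue medication is allowed throughout and this is the only planned look at its impact.

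**Working it through.** The plan gives no rescue-use rate, variance or target, so there is no figure of its own to reproduce. The check is on the order of events, followed by an illustration under stated assumptions.

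**1. Day one is the first-session day, after randomization.** The order is washout, eligibility confirmation, randomization, pre-procedure evaluation, then the procedure phase within one hour of that evaluation (Procedure Administration Protocol). Diary recording for the procedure phase starts on the day of the first session. No text limits the count to the hours before the session.

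**2. The 6-hour rule tilts the count toward later doses.** The VAS text in the Study Test Battery tells subjects to take no pain medication within 6 hours before a required rating, and allows a dose straight after one. On day one a rating is due in the pre-procedure evaluation and another within 10 minutes after the session. To keep the rule for both ratings, a subject takes nothing from 6 hours before the first until the second is done. If the first rating falls within 6 hours of waking, no waking hours remain for a compliant dose before the session. For that subject the count over waking hours is entirely post-session, whichever hours the plan meant. Washout ratings are made on waking, so there the restriction falls mainly on the preceding night. Day one is therefore not comparable with washout days or with later non-visit days.

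**3. How a same-day difference carries forward.** Let D be mean pre-treatment doses per day, the same in both arms by randomization, and let rA and rP be the signed proportional day-one changes on active and placebo. The mean day-one count is D(1 + r). With no true later difference, the contrast in change (later minus baseline, active minus placebo) is

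[D - D(1 + rA)] - [D - D(1 + rP)] = -D x (rA - rP).

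A restriction that acts equally in both arms cancels from rA - rP on average. All inputs below are assumptions:

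| rA - rP | D = 1 | D = 2 | D = 4 |
|---|---|---|---|
| -0.3 | +0.3 | +0.6 | +1.2 |
| -0.1 | +0.1 | +0.2 | +0.4 |
| 0 | 0 | 0 | 0 |
| +0.1 | -0.1 | -0.2 | -0.4 |
| +0.3 | -0.3 | -0.6 | -1.2 |

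A positive entry is the number of doses per day by which the active arm's relative reduction is understated; a negative entry overstates it.

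**4. One day against two.** With equal daily variances and between-day correlation rho, a two-day mean has (1 + rho)/2 of the variance of a single day: (1 + 0.3)/2 = 0.65, (1 + 0.5)/2 = 0.75 and (1 + 0.7)/2 = 0.85 for assumed rho of 0.3, 0.5 and 0.7. This is a side benefit of the washout mean.

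**The case against.** The strongest reply is that little depends on this count. The evaluation section names no change score, test or threshold, and rescue use is not among the listed supportive outcomes. Washout doses are recorded anyway, so a descriptive report could show them. The arms may also behave alike on day one: the trial is double-blind, the justification for the procedure protocol says the effect in low back pain develops slowly, and the Evaluation Time Point section describes a high early placebo effect. A 30-point same-day difference after one session fits poorly with that, and the outer rows of the table should not be read as likely. Washout use has its own weakness, since usual therapies have just stopped and the level may be untypical.

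All of this stands, and it sets the severity. It does not remove the point, because the plan still names the day-one count as the reference for change, and a count open to treatment influence is the wrong one to name. An untypical washout level applies to both arms alike.

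The word begins in the Daily Measures text might be taken to mean that no washout diary exists. The sentence sits under a phase heading, and the washout sections and Subject Daily Diary are explicit about earlier recording. This is loose wording only.

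**Conclusion.** The point holds, as a minor one. The baseline for rescue use is a single count after randomization, on the first-session day. It can include post-session doses, and for compliant subjects it leans toward them. Any effect on the between-arm contrast is -D x (rA - rP). Its size and sign are unknown, and it is zero if the arms respond alike on day one.

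Three stronger readings are not supported:

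- That the efficacy result is affected. The primary endpoint uses the washout VAS average, and neither the primary analysis nor the sample size uses the rescue count.
- That the plan hides a treatment effect on rescue use. This would need a between-arm difference on day one, for which the documents give no evidence.
- That the day-one count falls short of a full day by a calculable amount and so produces a false within-arm rise. The plan allows a dose straight after a rating, so doses may be delayed rather than lost.

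**What to change.** First, as a condition, reconcile the medication passages. The exclusion criterion on "Use of any one or more of the following analgesics, or an equivalent, within 7 days prior to commencement" of the procedures lists paracetamol, and the 48-hour washout lies inside those 7 days. The inclusion criterion has subjects refrain from pain medication "throughout the course of study participation, except for the specified study pain relief medication", the Washout Phase section starts as-needed rescue use, and Daily Measures names OTC Tylenol as the rescue product. These must be made to agree; this review takes no position on which rule is right.

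Then:

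- Define baseline rescue use as the mean daily count over the two washout diary days, matching the window for baseline VAS.
- Treat day one of the procedure phase as the first on-treatment day.
- Because washout use may be untypical, put the weight on between-arm comparisons rather than within-arm reductions.
- Tidy the diary wording so that the start date reads the same in every section.
- If the reconciled text leaves no rescue use in washout, report daily counts by arm without a change score.

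The cost is two or three sentences. No new visit or data item is needed if the washout diary runs as scheduled. Reconciling the medication passages is separate work and comes first.

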Compensation up to \$300
For qualified participants

Please contact <PI name> at
<test site name & location> at
<phone and/or e-mail> for details.

Compensation

A subject who completes his or her participation in this clinical study through to the final post-procedure administration visit will receive financial compensation of \$300.

A subject will not be charged for the cost of the study procedures with the Erchonia® FX-635™ Laser or for the cost of any other directly-related evaluations or measurements that occur as part of his or her participation in the study.

Sample size

There will be 64 qualified subjects enrolled in this clinical study:

- 32 subjects in the active procedure group
- 32 subjects in the control procedure group

Rationale for sample size

In the determination of sample size, the following parameters have been established for the purposes of assessing efficacy of the Erchonia® FX-635™ in this clinical study:

- Individual subject success criteria defined as a 30% or greater reduction in self-reported Degree of Pain rating on the 0-100 VAS from baseline to study endpoint evaluation.
- Overall study success criteria defined as a minimum 35% difference between the test device group and the placebo device group in the proportion of individual successes.
- It is anticipated that about 55% of subjects in the test device group and about 20% of subjects in the placebo device group will meet the individual success criteria, and
- Intended application of a two-tailed test with an alpha value of 0.05 and Power of 0.8

The **clinical relevance** of a 30% change in VAS score and a 35% difference in the proportion of individual successes between procedure groups has been well previously established over the past 8 years by FDA's Division of Surgical, Orthopedic and Restorative Devices through numerous pre-IDE reviews, the results of said studies that were subsequently used to successfully support various pain-reduction related indications for various Erchonia Corporation light therapy devices under Product Code NHN for the 510(k)s as listed below:

1. **K101430**; 06/22/10: "The FX-635™-AC DermaScanner™ is indicated, while using the red diodes, for adjunctive use in providing temporary relief of minor chronic neck and shoulder pain of musculoskeletal origin."
2. **K100509**; 06/08/10: "The Erchonia THL1 is indicated for use in providing temporary relief of minor chronic neck and shoulder pain of musculoskeletal origin."

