3. **K072206**; 04/24/08: "The Erchonia EML Laser is indicated for the temporary reduction in post - surgery pain at 24 hours after surgery following breast augmentation surgery."
4. **K050672**; 06/02/05: "The Erchonia EVRL Laser is generally indicated while using the red diode for adjunctive use in providing temporary relief of minor chronic neck and shoulder pain of musculoskeletal origin."
5. **K041139**; 09/30/04: "The Erchonia EML Laser is indicated as an adjunct to liposuction procedures of the thighs, hips and stomach for reduction of pain associated with the recovery process."

In consideration of the above parameters established for the purposes of sample size calculation, the sample size of 29 subjects per procedure group (test group and placebo group, separately) has been determined using the following reference calculator: *Hypothesis Testing: Categorical Data - Estimation of Sample Size and Power for Comparing Two Binomial Proportions* in Bernard Rosner's *Fundamentals of Biostatistics*.

It is anticipated that about one-twentieth of subjects overall may withdraw from the study prior to completion for various reasons. Therefore, the following formula is used to determine the final needed starting sample size for each group:

Final sample size = sample size X $1/(1-d)$; where $d = \# \text{ expected dropouts}/\# \text{ subjects enrolled}$.

Final sample size = $29 \times 1/(1-0.083)$

Final sample size = $29 \times 1/0.917 = 29 \times 1.0905 = 31.62$, rounded to 32 subjects per group.

Therefore, a minimum starting sample size of 32 subjects in each procedure group is needed to ensure that a sufficient number remains at the end of the trial (29 subjects per group) for any significant differences found between groups to be considered statistically valid and representative of the general population being sampled. This results in a total of 64 subjects being enrolled in this study across both study procedure groups.

STUDY PROCEDURE

STUDY TEST BATTERY

The following is a listing and description of the study measurement and assessment tools to be used and the variables to be recorded in this clinical study. At each evaluation point, the precise tools and variables from this list that will be employed will be specified.

QUALIFICATION EVALUATION TOOLS

THE SIMPLIFIED CALCULATED OSTEOPOROSIS RISK ESTIMATION (SCORE)

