- Oswestry Disability Index (ODI)/Oswestry Low Back Pain Questionnaire
- Range of Motion (ROM)
- Assessment Investigators' Adverse Events Evaluation

STUDY ENDPOINT EVALUATION: TWO MONTHS POST-PROCEDURE EVALUATION

- VAS Degree of Pain Rating
- Oswestry Disability Index (ODI)/Oswestry Low Back Pain Questionnaire
- Range of Motion (ROM)
- Subject Satisfaction With Study Outcome
- Subject Perceived Group Allocation and Rationale
- Assessment Investigator's Perceived Subject Group Allocation and Rationale
- Assessment Investigators' Adverse Events Evaluation

ADVERSE EVENTS

At each evaluation and procedure administration test site visit throughout the clinical study, and at any other time throughout the duration of the clinical trial that is necessary, any and all potential adverse events reported by a subject or observed by an investigator will be recorded on the case report form, and subsequently evaluated by a suitably qualified independent reviewer for determination of relationship to the study treatment and whether or not any corrective action needs to be taken. All potential adverse events recorded will be appropriately reported to the governing IRB, as applicable.

It is unlikely and not expected that any adverse events will result from implementation of this clinical study protocol. Prior clinical trials using low level laser light have not typically yielded any adverse events or reactions. However, potential adverse events that may feasibly occur from application of the Erchonia® FX-635™ include, but are not necessarily limited to: skin irritation, discoloring, rash, indentations and infection.

STATISTICAL ANALYSIS

PRIMARY EFFICACY OUTCOME MEASURE: CHANGE IN SUBJECT SELF-REPORTED VAS PAIN RATING FROM BASELINE TO STUDY ENDPOINT

Primary efficacy outcome measure for this clinical study will be a statistically significant difference in the proportion of subjects between test and control groups who achieve a clinically meaningful and statistically significant decrease in self-reported VAS pain rating from baseline to study endpoint.

Subjects meeting Individual Success Criteria

The individual subject success criteria is defined as a 30% or greater decrease in self-reported VAS pain rating at study endpoint relative to baseline.

Overall Study Success Criteria.

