Overall study success criteria is defined as at least a 35% difference between procedure groups, comparing the proportion of individual successes in each group. It is anticipated that about 55% of subjects in the test group will meet the individual success criteria and about 20% of subjects in the control group will meet the individual success criteria.

The clinical relevance of a 30% change in VAS score has been well previously established by FDA's Division of Surgical, Orthopedic and Restorative Devices through numerous pre-IDE reviews, the results of said studies that were subsequently used to successfully support various pain-reduction related indications for various Erchonia Corporation light therapy devices under Product Code NHN for the 510(k)s listed below over the past 8 years:

1. K101430; 06/22/10: "The MLS-AC DermaScanner™ is indicated, while using the red diodes, for adjunctive use in providing temporary relief of minor chronic neck and shoulder pain of musculoskeletal origin."
2. K100509; 06/08/10: "The Erchonia THL1 is indicated for use in providing temporary relief of minor chronic neck and shoulder pain of musculoskeletal origin."
3. K072206; 04/24/08: "The Erchonia EML Laser is indicated for the temporary reduction in post-surgery pain at 24 hours after surgery following breast augmentation surgery."
4. K050672; 06/02/05: "The Erchonia EVRL Laser is generally indicated while using the red diode for adjunctive use in providing temporary relief of minor chronic neck and shoulder pain of musculoskeletal origin."
5. K041139; 09/30/04: "The Erchonia EML Laser is indicated as an adjunct to liposuction procedures of the thighs, hips and stomach for reduction of pain associated with the recovery process."

Evaluation Time Point

The study end evaluation time point at which study success will be analyzed is at two months post-procedure evaluation relative to baseline evaluation.

The rationale and validation for the timing of the study endpoint is based a combination of factors, as follows:

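### Study success needs an observed difference of at least 35 points, which is the assumed effect itself, so its probability is about 50% rather than the stated 80%, and a significant result below 35 points has no settled verdict

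*Combined protocol and SAP*

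**What the plan says.** The success bar appears twice. Under Rationale for sample size: "Overall study success criteria defined as a minimum 35% difference between the test device group and the placebo device group". Under Overall Study Success Criteria in the Statistical Analysis section: "Overall study success criteria is defined as at least a 35% difference between procedure groups, comparing the proportion of individual successes in each group". The latter section then anticipates that "about 55% of subjects in the test group will meet the individual success criteria and about 20% of subjects in the control group" will do so. Since 55 − 20 = 35, the percentage must mean absolute points.

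The sample size rests on "Intended application of a two-tailed test with an alpha value of 0.05 and Power of 0.8", and "the sample size of 29 subjects per procedure group (test group and placebo group, separately) has been determined using the following reference calculator". The same section inflates 29 to 32 per group for dropout and says that 29 remaining per group are needed "for any significant differences found between groups to be considered statistically valid". It also presents the 35-point difference as clinically relevant on the strength of earlier regulator reviews: "a 35% difference in the proportion of individual successes between procedure groups has been well previously established".

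The primary outcome is worded differently: "Primary efficacy outcome measure for this clinical study will be a statistically significant difference in the proportion of subjects between test and control groups". It sets no minimum between-group difference, and Expected Results likewise forecasts only a significantly greater proportion. Under Hypotheses, the null is the absence of a significant difference, while the alternative is a significant difference of 35% or more. The statistical methods then list two items under the primary analysis: Fisher's exact test on the responder proportions and an ANCOVA of VAS change.

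**The concern.** If the bar for the observed difference is set at the assumed true difference, the estimate falls on either side of it about equally often. More subjects narrow the spread around 35 points but do not move its centre. A reader who sees one probability in the plan, 80%, can take it for the chance that the study succeeds.

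The second problem is the result that is significant but below 35 points. It fails the overall success criterion and meets the primary outcome measure. It contradicts the null as worded without satisfying the alternative. No sentence says which statement governs, or whether the ANCOVA has any bearing on success. The trial is meant to support a 510(k) submission, so the verdict on such a result could be argued after the data are known.

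**Working it through.** **Inputs.** p1 = 0.55, p2 = 0.20, two-sided alpha 0.05, power 0.80, 29 per group, 32 enrolled per group (Sample size and Rationale for sample size); bar of 35 points (Overall Study Success Criteria); Fisher's exact test (Primary Efficacy Outcome Statistical Evaluation Methods).

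**1. The plan's own figure.** With pooled variance and no continuity correction,

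n = [z(0.975)·√(2·p̄·q̄) + z(0.80)·√(p1·q1 + p2·q2)]² / (p1 − p2)²

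Here p̄ = 0.375, √(2 × 0.375 × 0.625) = 0.6847 and √(0.2475 + 0.1600) = 0.6384. So n = (1.960 × 0.6847 + 0.8416 × 0.6384)² / 0.1225 = 28.8, rounded up to 29. Power at 29 is Φ[(0.35·√29 − 1.960 × 0.6847) / 0.6384] = 80.2%. The stated figure reproduces, as power against no difference.

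**2. Chance of reaching the bar.** The observed difference is centred on 0.35, with standard error √(0.4075/32) = 0.113 at 32 per group. In the normal approximation, P(difference ≥ 0.35) = P(Z ≥ 0) = 50% for every n. Exact values come from summing Binomial(n, 0.55) × Binomial(n, 0.20) over all outcomes. Fisher significance means two-sided p ≤ 0.05 in favour of the device.

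| n per group | Responder margin needed | P(≥ 35 points) | Fisher power | P(significant, below 35 points) |
|---|---|---|---|---|
| 29 | 11 (37.9 points) | 46.5% | 71.3% | 24.8% |
| 30 | 11 (36.7) | 50.6% | 73.8% | 23.2% |
| 31 | 11 (35.5) | 54.5% | 76.1% | 21.6% |
| 32 | 12 (37.5) | 47.2% | 78.3% | 31.1% |

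Over all 16 combinations of group sizes 29 to 32, the three ranges are 46.5–54.5%, 71.3–81.8% and 21.6–31.5%. The change from 31 to 32 comes from discreteness: 0.35 × 32 = 11.2, so 12 more responders are needed, and a margin of exactly 11 (34.4 points) has probability 11.0%. Larger trials do not help: P(≥ 35 points) is 53.4% at 100 per group and 51.1% at 1000.

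**3. Overlap of the two rules.** In all 16 combinations every result of at least 35 points is also Fisher-significant. Requiring both therefore gives the same success probability as the 35-point rule alone.

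**4. An example.** 17/32 against 6/32 is a difference of 34.4 points with Fisher p = 0.008 and Newcombe 95% interval 10.9 to 53.2 points. It meets the primary outcome measure and fails the success criterion.

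**5. False positives.** With equal true rates of 20% to 50% at 32 per group, the 35-point rule is met in 0.02–0.18% of trials, against 1.2–1.6% for Fisher significance favouring the device.

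**6. Sensitivity to the rates at 32 per group.** P(≥ 35 points) is 30% at 50/20, 31% at 55/25, 65% at 60/20 and 65% at 55/15.

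**The case against.** The strongest reply is that the documents do give a verdict. Overall success is defined twice in the same terms, the alternative hypothesis agrees, and the primary outcome paragraph names a measure rather than a success rule. On that reading a significant result below 35 points is simply a failure. The power figure is attached to a two-tailed test, is correct for the approximate test, and is never called the probability of success. Requiring an observed effect as large as a clinically relevant difference is a legitimate, conservative choice, and its cost falls on the sponsor. The primary analysis is also intent-to-treat with last observation carried forward, so the analysed number should be near 32 per group, where Fisher power is close to 0.8.

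Much of this stands. The bar itself is defensible, and applied as written it does not raise the false-positive rate. The figure of 78.3% at 32 is the more relevant one if few subjects are lost from the analysis set, although the plan's own sizing argument relies on 29 remaining. The success probability also depends on rates that the plan gives only as approximate.

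It does not remove the gap. The primary outcome paragraph in the same section is worded as significance alone, nothing ranks it against the 35-point rule, and the hypotheses leave the in-between result outside both statements. The plan gives no probability for the success that it defines.

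**Conclusion.** The concern holds and should be fixed. If the true rates are 55% and 20%, the probability of study success as defined is about 50% (47.2% at 32 per group), against the only stated figure of 80%. That 80% does not describe the planned Fisher test either. Between about one in five and one in three trials would fall in the region where the plan's statements point to different verdicts. These figures assume independent binomial outcomes and 29 to 32 analysed per group; if the true rates differ, step 6 of the working shows how far the success probability moves. The main risk is reinterpretation after the results are known, not a raised false-positive rate.

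**What to change.** State one decision rule in the primary outcome measure, Overall Study Success Criteria and Hypotheses, consistent with Rationale for sample size.

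- **A (default, because it keeps the documents' explicit criterion).** Study success requires Fisher's exact p ≤ 0.05 in favour of the device and an observed difference of at least 35 points. A significant result below 35 points is reported as significant but not a study success. Under Rationale for sample size, state that the probability of success at 55% and 20% is about 50% (47% at 32 per group), that 0.8 refers only to the approximate test of no difference, and that Fisher power is 71% at 29 and 78% at 32 per group.
- **B (only if 35 points was meant purely as the planning effect).** Study success is Fisher's exact p ≤ 0.05 in favour of the device. Replace the 35-point criterion in both places where it is defined, remove the 35% condition from the alternative hypothesis, report the difference with its 95% confidence interval beside the 35-point benchmark, and restate power as 71% at 29 and 78% at 32.

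Under either option, say that the ANCOVA is supportive and does not decide study success.

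The cost is wording only, with no extra subjects, but the stated probabilities become less favourable than 80%. Option A leaves the bar where it is. Option B lowers it, and because the plan ties the 35-point difference to earlier regulator reviews, it may need regulator agreement.
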